#### Acute protocols (Visits 5 + 6)

On visit 5 participants will arrive at the laboratory at approximately 0640 after a 10h overnight fast. After a brief assessment, subjects will rest on a bed for 3 hours. After this period, a skeletal muscle biopsy will be obtained and participants will perform a bout of resistance exercise with a randomised leg, followed by a bout of endurance exercise. Skeletal muscle biopsies will again be obtained immediately following both bouts of exercise and again 3h following exercise. On visit 6, participants will again arrive at the laboratory at approximately 0640 after an overnight fast. This time, a catheter will be placed in the upper forearm. After the placement of the catheter, a primed constant infusion of L-[*ring*-C6] phenylalanine will be commenced to measure rates of MPS and a catheter placed in the contralateral arm for repeated blood sampling. Exercise and skeletal muscle biopsies will be obtained as in visit 5 (see Figure 2). We have routinely obtained ethical approval and published papers for studies that employ skeletal muscle biopsies and stable amino acid tracers in human volunteers (3, 14, 44-49). [name], a licenced physician, has approved our standard operating procedure and will oversee all muscle biopsy and catheter infusions.

[figure not shown]
[figure not shown]

Figure 1 Schematic illustration of experimental design.

**R.Ex-** 3 sets  $\times$  10 reps 70% 1RM leg press followed by leg ext.  
2 min recovery between sets and exercises.

**E.Ex-** 4  $\times$  5 min @ 65% single leg peak power  
w/ 2.5 min recovery @ 20% peak power.

\* Timing will change depending on exercise order

Figure 2. Schematic illustration of Visit 6.

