## Specific Objectives

1. Our primary objective is to examine the effect of resistance exercise on the human skeletal muscle phosphoproteome.
2. Our secondary objective is to assess changes in rates of myofibrillar and mitochondrial MPS following resistance and endurance exercise.

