## **Methodology**

A schematic illustration of the experimental design and experimental trial can be seen in Figures 1 and 2, respectively. In a within-subject repeated measures cross-over design, 12 participants (6 male and 6 female) will attend the laboratories at the Dept. of Kinesiology on 6 separate occasions. On the first occasions participants will be assessed for body composition using dual-energy x-ray absorptiometry (DXA) after an overnight fast (~10 hours) followed by familiarization on resistance exercise and endurance exercise equipment. At this point, your two legs will be randomly assigned to the resistance exercise or endurance exercise group.

On the second visit, participants will perform a 1-repetition maximum test on a leg press and leg extension machine. These tests will be used to determine the workload performed on the experimental trials. On the third visit participants will perform a  $V_{02\text{ max}}$  test on a cycle ergometer to determine their aerobic fitness. On the same day, subjects will be familiarized with single-leg cycling. On visit 4, subjects will perform another  $V_{02\text{ max}}$  test on a cycle ergometer using one leg only. This test will determine the intensity of cycling performed on the experimental trial. To ensure the intensity is appropriate, the subjects will be familiarized with the experimental trial training programs (see “Exercise protocols” below).

Subjects will then embark on a 3-day period of controlled diet and exercise followed by experimental trials (visits 5 and 6) separated by 1 week. The reason for the two independent trials is that the measurement of MPS requires the

infusion of a stable amino acid isotope (L-[*ring*-C6] phenylalanine), which interferes with the assessment of the phosphoproteome due to the fact they both detect changes in protein mass. Thus the first trial will be conducted to assess exercise-induced changes in the phosphoproteome and the second for MPS, using the L-[*ring*-C6] phenylalanine isotope.

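### Visit 6: the text fixes resistance before endurance while the Figure 2 note implies that order varies; if the text is followed, modality cannot be separated from bout order in the MPS contrasts of hypotheses 2 and 3

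*Combined protocol and SAP*

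**What the plan says.** The Methodology section describes a within-subject design in 12 participants, 6 male and 6 female, in which "your two legs will be randomly assigned to the resistance exercise or endurance exercise group". There are two experimental visits: "Thus the first trial will be conducted to assess exercise-induced changes in the phosphoproteome and the second for MPS". MPS by infused tracer therefore comes from visit 6.

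For visit 5, the Acute protocols section states that "participants will perform a bout of resistance exercise with a randomised leg, followed by a bout of endurance exercise". On sampling it says: "Skeletal muscle biopsies will again be obtained immediately following both bouts of exercise and again 3h following exercise". For visit 6 it says: "Exercise and skeletal muscle biopsies will be obtained as in visit 5 (see Figure 2". The note placed directly above the Figure 2 caption, which identifies that figure as visit 6, reads "Timing will change depending on exercise order".

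Under Specific Objectives, the primary objective is worded "Our primary objective is to examine the effect of resistance exercise on the human skeletal muscle phosphoproteome". The secondary objective is to "assess changes in rates of myofibrillar and mitochondrial MPS following resistance and endurance exercise". Hypothesis 2 expects the larger myofibrillar MPS response after resistance exercise, and hypothesis 3 the larger mitochondrial response after endurance exercise.

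The readable text does not allocate, balance or adjust for the order of the two bouts. The figure images are not available here and may hold such a scheme.

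**The concern.** The visit 6 text and the visit 6 figure note cannot both govern the order of the bouts. The difference matters because hypotheses 2 and 3 compare the two legs directly. Under the text, the leg assigned to endurance is always the second one exercised. Anything that differs between first and second place then enters the modality contrast in full: the systemic response to the earlier bout, time since the start of infusion, and time since the pre-exercise biopsy. Randomising which leg does which exercise balances leg characteristics such as dominance, but it leaves order untouched. A fixed order cannot be repaired in the analysis.

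The 3 h sample raises a related ambiguity. The sampling sentence can mean one common clock for both legs or a separate clock for each. The figure note is compatible with separate clocks.

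**Working it through.** The plan states no figure on this point, so there is none to reproduce. The checks below use its design.

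**1. Aliasing.** Inputs: 12 participants, two legs each, one modality per leg (Methodology). Model: participant effects (12 columns) + modality + order = 14 columns.

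- Resistance first in all 12: rank 13 of 14, modality–order correlation 1.00. Modality is not estimable apart from order. The two columns coincide whatever the number of participants.
- Resistance first in 6 of 12: rank 14 of 14, correlation 0.

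**2. Share of an order effect in the unadjusted contrast.** Let M be the modality effect and O the first-minus-second effect. The expected resistance-minus-endurance difference is M + O when resistance comes first and M − O when it comes second. With k of n participants resistance-first, the mean is M + O(2k−n)/n.

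| Resistance-first : endurance-first | (2k−n)/n | Share |
|---|---|---|
| 12:0 | 12/12 | 100% |
| 9:3 | 6/12 | 50% |
| 8:4 | 4/12 | 33% |
| 6:6 | 0/12 | 0% |

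**3. Illustration only.** The documents give neither the size of an order effect nor a test. Assume a two-sided 5% paired t-test, n = 12, no true modality difference, resistance always first, and an order effect of d SD of the paired differences. The statistic is then noncentral t with 11 df and noncentrality d√12.

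- d = 0.1: noncentrality 0.346, rejection 6.2%
- d = 0.25: noncentrality 0.866, rejection 12.4%
- d = 0.5: noncentrality 1.732, rejection 35.3%

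Under the same assumptions, simulation at 8:4 unadjusted gives 5.1% (d = 0.25) and 5.5% (d = 0.5). At 6:6 with an order term it gives 5.0% for both. At 6:6 without the term it gives 4.4% and 3.0%: unbiased but conservative.

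**4. Clock.** The endurance bout is 4 × 5 min with 2.5 min recoveries (Figure 1 and 2 notes; Exercise Protocol). That is 4×5 + 3×2.5 = 27.5 min, or 4×5 + 4×2.5 = 30 min if a recovery follows the last interval. Only if resistance is first and the 3 h clock runs from the end of the second bout is the resistance leg sampled at least this much later after its own exercise: 27.5/180 = 15% to 30/180 = 17% of the window. On leg-specific clocks the offset is 0. Dividing by t in the MPS equation corrects the length of the interval, not which part of recovery it covers.

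**5. Biopsy count.** One pre-exercise sample, one immediate sample per leg and one 3 h sample per leg make 1 + 2 + 2 = 5. The Skeletal Muscle Biopsies section gives four on day 0. Leg-specific windows cannot simply be assumed feasible.

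**6. Visit 5 under the text.** An immediate resistance-leg sample is free of cycling only if it is taken before the endurance bout. The 3 h resistance-leg sample and every post-exercise endurance-leg sample follow both bouts.

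**The case against.** The strongest reply is that the only order statement specific to visit 6 is the Figure 2 note, and it points to a varying order. The figure itself may show the allocation and the clocks. If so, the consequences are mild: none at 6:6, and little effect on the illustrative rejection rate at 8:4. This stands as a reason for caution. A reader might infer that the trial does use a fixed order, or that the plan has no order scheme, and the documents do not establish either. What survives is that the text says otherwise, and a site following it would produce a contrast that cannot be repaired.

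A second reply is that the rejection rates rest on an invented order effect and an unspecified test. This also stands. A reader might take 12% or 35% as the trial's false-positive rate, but the documents support no such figure. Moreover, hypotheses 2 and 3 predict opposite signs for resistance minus endurance. An order effect of the same sign in both protein fractions would favour one hypothesis and work against the other, so it could not falsely confirm both.

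Third, this is a secondary objective in a study that calls itself an observational pilot. That limits the weight of the point. It does not remove it, because both hypotheses are stated as directional comparisons between modalities.

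**Conclusion.** The conflict between the Acute protocols text and the Figure 2 note is real and should be fixed. If the text governs visit 6, modality and bout order are completely aliased in the MPS contrasts of hypotheses 2 and 3, at any sample size. If order varies, the unadjusted contrast carries (2k−n)/n of any order effect and the contrast is estimable. Whether bias follows, and how much, depends on an order effect that the documents do not quantify. The D2O measure of MPS over days would share the aliasing wherever it compares legs exercised in a fixed order, although a half-hour offset is negligible on that scale.

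Two inferences about visit 5 and the primary objective should be avoided. One is that resistance first leaves the primary objective untouched. It protects at most the immediate resistance-leg sample, and only if that is taken before cycling. The other is that the primary objective is undermined as a whole. It concerns the effect of resistance exercise and does not need the between-leg contrast. Hypothesis 1 also covers endurance exercise, however, and under the text those samples always follow both bouts.

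Confidence is medium because Figure 2 could not be seen.

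**What to change.** Check Figure 2 and reconcile the Acute protocols text with its note. Then, unless the figure already settles these points:

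- **Order at visit 6.** State that bout order is randomised and balanced 6:6, with 3:3 within each sex.
- **Analysis.** Include order as a term in the paired MPS analysis. At 6:6 the term recovers efficiency and nominal test size; it is not needed to remove bias. After attrition it removes the residual imbalance: losing one or two participants from one order group leaves a share of 1/11 = 9% or 2/10 = 20%, at a variance inflation of 1/(1 − share²) = 1.01 or 1.04.
- **Clock.** State which bout starts each leg's 3 h clock, and use recorded times for t. Reconcile any leg-specific windows with the four day-0 biopsies, without adding biopsies.
- **Visit 5.** State the order there too; the choice is the sponsor's.

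The direct cost is one order list and one residual degree of freedom. Going from 11 to 10 df moves the critical value from 2.201 to 2.228, a ratio of 1.012, so intervals are about 1.2% wider at the same residual SD.

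There is also a trade-off. If visit 5 stays resistance-first, order will differ between visits for half the participants, which weakens the link between phosphoproteome and MPS results. Using the same balanced order at both visits avoids that but gives up the protected immediate resistance sample in half of them.

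If the sponsor keeps a fixed order, hypotheses 2 and 3 should be reported as unable to separate modality from order.

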## Rationale

Skeletal muscle is a highly plastic tissue, capable of adapting to changes in nutritional intake and contractile activity. For instance, resistance exercise results in a mild stimulation of rates of muscle protein breakdown (MPB) but a greater stimulation of the rates of muscle protein synthesis (MPS) (1-3). When resistance exercise is performed prior to protein ingestion there is a synergistic combination of the two stimuli such that rates of MPS are stimulated over and above those of MPB (4-6). Thus, repeated bouts of resistance exercise, when coupled with protein ingestion, result in the accretion of skeletal muscle protein referred to as hypertrophy (7). Importantly, by changing the nature of the exercise stimulus, it is possible to redirect the focus of the type of skeletal muscle proteins that are being synthesised. For example, we know that prolonged and repeated lower-load dynamic stimulation of skeletal muscle (*i.e.*, endurance exercise training) results in an increase in the expression of mitochondrial genes (8), proteins (8-10), and ultimately enhanced mitochondrial content (11), leading to a shift towards an oxidative phenotype, and improved fatigue resistance (12). Resistance exercise training also stimulates the transcription of genes and accrual of new muscle proteins (13, 14), but these genes and proteins are largely associated with the myofibrillar protein fraction, and regular resistance exercise leads to muscle hypertrophy and increased force-generating capacity (15, 16). However, during the early stages of exercise training, particularly in training-naïve participants there is a significant increase in the expression of genes common to both modalities of exercise (17, 18). It is only with sustained exercise training that there is a ‘fine tuning’ of the transcriptome, the protein synthetic response, and then the proteome that gives rise to divergent hypertrophic and oxidative phenotypes (17, 19).

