## Hypotheses

We hypothesize that:

1. Both resistance exercise and endurance exercise will result in the widespread phosphorylation of proteins involved in the regulation of energy metabolism, transcription, translation and muscle protein synthesis.
2. Resistance exercise will increase myofibrillar MPS to a greater extent than endurance exercise.
3. Endurance exercise will increase rates of mitochondrial MPS to a greater extent than resistance exercise.

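### No unexercised muscle is sampled at the later time, so a rest-to-3 h change cannot on its own be reported as an effect of exercise

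*Combined protocol and SAP*

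**What the plan says.** The primary objective (Specific Objectives) is causal in form: "Our primary objective is to examine the effect of resistance exercise on the human skeletal muscle phosphoproteome". Hypothesis 1 likewise expects each exercise mode to produce phosphorylation. Hypotheses 2 and 3 compare modes; the first of these reads "Resistance exercise will increase myofibrillar MPS to a greater extent than endurance exercise".

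Under Methodology, "your two legs will be randomly assigned to the resistance exercise or endurance exercise group", so neither leg is kept at rest.

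Acute protocols (Visits 5 + 6) gives the order of events. "On visit 5 participants will arrive at the laboratory at approximately 0640 after a 10h overnight fast". Three hours of bed rest come next. One resting biopsy follows (the leg is not stated), then the resistance bout in one leg, then the endurance bout. After that: "Skeletal muscle biopsies will again be obtained immediately following both bouts of exercise and again 3h following exercise". Visit 6 repeats the exercise and biopsies with the phenylalanine tracer running.

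The biopsy section lists seven samples, four of them on day 0, and identifies none as a rested-leg or time-matched control. It calculates the resting tracer MPS rate from a pre-infusion blood sample, so that rate refers to the period before exercise. No analysis section says which time point or contrast carries the claim about exercise.

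**The concern.** For every participant the resting sample comes first, and both legs have been exercised by the time of the 3 h sample. In a comparison of rest with 3 h, having exercised and being later in the day are the same variable. So are time since the first biopsy and, if no food is given, hours fasted. No model fitted to these samples can separate them, and recruiting more participants would not help.

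The protocol's own Rationale describes muscle as "capable of adapting to changes in nutritional intake and contractile activity", so it names nutrition alongside contraction as something muscle responds to. A phosphosite that drifts over the morning for a reason unrelated to exercise would change from rest to 3 h in both legs and could be listed as exercise-regulated. The resting and post-exercise tracer MPS periods at visit 6 come in the same fixed order and share the problem.

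**Working it through.** **1. Which contrasts have a concurrent comparator**

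| Contrast | Comparator at the same time? | Consequence |
|---|---|---|
| Rest to 3 h, either leg | None | Exercise fully aliased with elapsed time |
| Rest to post-exercise infusion MPS (visit 6) | None | Same |
| Rest to immediately post-exercise | None | Same in kind, over a much shorter interval |
| Resistance leg versus endurance leg at 3 h | The other leg | Shared drift largely cancels |

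**2. Length of the gap at visit 5**

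The plan states no elapsed time between the resting and 3 h biopsies, so it is rebuilt from the stated durations. Inputs are the 10 h fast and 3 h rest (Acute protocols) and the two exercise prescriptions. One assumption is added: each set of 10 repetitions takes 20 to 40 s. Time for the brief assessment and the biopsies is ignored.

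- Resting biopsy: 10 + 3 = 13 h fasted, at about 09:40.
- Resistance bout, figure text (3 sets of each of two exercises): 6 sets and 5 recoveries of 2 min, so 10 min plus 2 to 4 min of lifting = 12 to 14 min.
- Resistance bout, Exercise Protocol (5 sets of each): 10 sets and 9 recoveries, so 18 min plus 3.3 to 6.7 min = 21.3 to 24.7 min.
- Endurance bout: 4 × 5 + 3 × 2.5 = 27.5 min, or 30 min with a fourth recovery.

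The text does not say when the 3 h clock starts.

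| 3 h timed from | Shortest | Longest |
|---|---|---|
| End of resistance bout, done first | 13 + 12/60 + 3 = 16.2 h | 13 + 24.7/60 + 3 = 16.4 h |
| End of second bout | 13 + 39.5/60 + 3 = 16.7 h | 13 + 54.7/60 + 3 = 16.9 h |

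The gap is therefore 3.2 to 3.9 h. Relative to 13 h, 3.2/13 = 25% and 3.9/13 = 30%. The percentage applies to fasting only if no food is given between the two biopsies.

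**3. What such a gap could do (illustration only)**

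Take a true exercise effect of zero and a drift of d standard deviations of the paired change. A two-sided paired t-test at 0.05 has a noncentral t distribution with n − 1 degrees of freedom and noncentrality d√n. The chance that one phosphosite is declared changed from rest to 3 h is:

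| Assumed d | n = 6 | n = 12 |
|---|---|---|
| 0 | 5% | 5% |
| 0.25 | 8% | 12% |
| 0.5 | 17% | 35% |
| 0.75 | 32% | 66% |
| 1.0 | 51% | 88% |

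The error grows with sample size, as expected of a bias. In a simulation (20,000 replicates, n = 12, independent leg changes, shared drift) the between-leg test rejected in 4.9%, 5.1% and 5.1% of replicates at d = 0, 0.5 and 1.0. The documents give neither a drift value nor a test level; both are assumptions here.

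**4. Hypotheses 2 and 3**

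With one shared resting value, (resistance − rest) − (endurance − rest) = resistance − endurance. The resting term cancels, so these comparisons do not depend on it.

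**5. Is the between-leg contrast available?**

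One resting biopsy plus two legs at two post-exercise times is 1 + 2 × 2 = 5. The biopsy section gives 4 for day 0. If 4 is right, one leg may be missing at one time point.

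**The case against.** The strongest reply is that the plan never designates the rest-to-3 h change as the effect of resistance exercise. The objectives and hypotheses name no time point, an immediate post-exercise biopsy is planned, and Sample Size calls the study an observational pilot, with sampling modelled on earlier before-and-after work. This is fair, and it rules out reading the plan as committed to the confounded contrast. But with causal wording and no stated contrast, nothing prevents the 3 h results from being reported that way, and the pilot label does not remove the bias.

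Second, the longer fast is an inference. The figures that carry the visit schedule are not readable, and the diet section says food is provided without giving times. This stands: only elapsed time and repeated biopsy are certain. If food were given, feeding would take the place of fasting as the rival explanation.

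Third, nothing in the documents shows that any phosphosite drifts over these hours. Hypothesis 1 predicts widespread change across several protein classes, so one drifting site would not establish it. This also stands; the percentages above are not evidence of drift.

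Fourth, the alternatives are imperfect. If biopsies wait for both bouts, the resistance leg's immediate sample also follows the other leg's endurance work. If 3 h is timed per leg, the legs are offset by about one bout. If resistance always comes first, as the text has it (the figure note suggests that order varies), the between-leg contrast also carries an order effect. These points limit how the fix may be worded but do not defeat it.

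**Conclusion.** The point holds for the rest-to-3 h phosphoproteome change and the rest-to-post infusion MPS change. Both are aliased with elapsed time and repeated biopsy. At visit 5 the elapsed time is about 3.2 to 3.9 h, given the assumed set durations and either reading of the 3 h clock. The absence of a rested comparator follows from the text alone; the added fasting depends on no food being given. The bias per site cannot be sized.

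A reader might infer more than the documents support:

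- *That the 3 h biopsy is at least 16.6 h into the fast.* If the clock starts at the end of each leg's own bout, it can be about 16.2 h.
- *That rest versus immediately post-exercise is clean and should be the sole basis for the exercise effect.* It is only less confounded by time and may include the other leg's bout.
- *That the two legs are at exactly the same clock time at 3 h.* This depends on how 3 h is timed.
- *That hypotheses 2 and 3 are undermined.* They compare modes, and a shared resting value cancels.
- *That all MPS results are affected.* The deuterated-water measure is integrated over days, so a shift of a few hours hardly applies to it.

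**What to change.** - In Specific Objectives and Acute protocols (Visits 5 + 6), state that rest-to-3 h phosphoproteome changes and rest-to-post infusion MPS changes will be reported as *change from rest*, not on their own as an effect of exercise. State also that at 3 h only between-leg differences will be attributed to exercise mode.
- For the primary objective, identify rest versus immediately post-exercise as the less time-confounded contrast. Say that it is not unconfounded and that the immediate sample may follow the other leg's bout.
- State whether 3 h runs from each leg's own bout or from the second bout. Sample both legs at matched times, or record the offset.
- Reconcile the day-0 biopsy count (4 in the biopsy section, 5 implied by Acute protocols if both legs are sampled at both post-exercise times) so that the between-leg contrast is known to be available. The resistance bout (3 sets at 70% 1RM in the figure text, 5 sets at 75% in Exercise Protocol) also needs reconciling, since it affects the timing.

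The relabelling and choice of contrast need no extra samples, participants or visits. The cost is a weaker claim for the 3 h versus rest results. If the count reconciles to 4, the plan should say which between-leg contrast is lost.
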